1.5 BN101-101 Study

BN101-101 is a randomized, double-blind phase I clinical study conducted in Chinese healthy volunteers to evaluate the tolerability, safety and pharmacokinetic (PK) profile of different dose levels of BN101/belumosudil administered as a single dose in healthy volunteers. A total of 2 study cohorts were enrolled: cohort 1 (BN101/belumosudil or placebo 200 mg single oral dose) and cohort 2 (BN101/belumosudil or placebo 400 mg single oral dose). A total of 85 subjects were screened for this study; 24 subjects were enrolled in the study and underwent randomization, 23 received study drug administration, 23 completed the study, and 1 subject withdrew early due to an adverse event prior to drug administration. Eleven subjects in cohort 1 received study medication and completed the study, of which 8 received BN101 and 3 received placebo; 12 subjects in cohort 2 received study medication and completed the study, of which 9 received BN101 and 3 received placebo.

The 23 subjects included in the modified intention to treat analysis set (mITT) had a mean (range) age of 31.7 (20-43) years, 73.9% were male and 26.1% were female, a mean (range) body weight of 62.76 (49.4-78.5) kg, and a mean (range) BMI of 22.13 (19.5-23.9) kg/m².

A total of 4 (17.4%, 4/23) subjects reported 4 TEAEs during the study period; PTs reported by subjects receiving BN101 included: decreased body mass index, positive urine leukocytes, and elevated blood triglycerides (1 subject each, 5.9%); PTs reported by subjects receiving placebo included: abnormal electrocardiogram T waves (1 subject, 16.7%). All TEAEs were grade 1, and no subject had a grade 2 or higher TEAE.

No serious adverse events or deaths were reported during the study period, and no subjects withdrew early from the study due to AE. No clinically significant laboratory test abnormalities were noted during the study period, with the exception of positive urine leukocytes and elevated blood triglycerides (1 subject each receiving BN101, 5.9%). No subject was found to have a QTcF interval value of \geq 450 ms or a QT interval of \geq 480 ms, and no subject had a change in QTcF interval from baseline of \geq 30 ms after dosing. Overall, BN101 was well tolerated as a single dose at 200 mg and 400 mg, and no unintended safety events were observed. Overall, BN101 has a favorable safety profile in healthy Chinese subjects.

The PK parameters of plasma BN101 in the subjects are shown in Table 2. BN101 was rapidly absorbed after a single oral dose, peaking at a median of 1.5 hours (range: 0.5-2.0 hours); the elimination half-life was highly variable, with a median elimination half-life of 10.35 hours and 8.92 hours at the 200 mg dose and 400 mg dose, respectively. Overall, the AUC₀₋₂₄ of BN101 increased slightly with dose, but was lower than dose proportionality, with a mean AUC₀₋₂₄ of 9040.44 ng*h/mL at the 200 mg dose and 9984.00 ng*h/mL at the 400 mg dose, respectively. The C_{max} was similar in the

2 dose cohorts, with a mean C_{max} of 2355.02 ng*h/mL at the 200 mg dose and 2355.02 ng*h/mL at the 400 mg dose, respectively.

Table 2 Plasma BN101/belumosudil pharmacokinetic parameters-PK analysis set

Trantmant	_	PK Parameters				
Treatment group	Statistic	AUC_{0-24}	$\mathrm{AUC}_{0\text{-}\infty}$	C_{max}	$T_{1/2}$	T_{max}
		(ng*h/mL)	(ng*h/mL)	(ng/mL)	(h)	(h)
BN101 200mg (N=8)	Median	6883.41	7635.11	2204.59	10.35	1.50
	Minimum	4057.36	4490.96	976.96	2.13	0.5
	Maximum	18074.16	19561.24	4265.25	48.01	2.0
	Arithmetic mean	9040.44	10055.32	2355.02	14.28	/
	Coefficient of variation	58.64	59.39	45.53	103.52	/
BN101 400mg (N=9)	Median	8120.87	10264.37	2181.44	8.92	1.50
	Minimum	4426.67	4837.27	941.48	3.85	0.5
	Maximum	19691.89	20375.86	3939.14	28.69	2.0
	Arithmetic mean	9984.00	10981.49	2315.84	11.80	/
	Coefficient of variation	56.21	51.12	48.25	69.22	/

N is the number of subjects entering the analysis set in each group.

1.6 Rationale for the design of this study

As BN101/belumosudil has completed clinical development for cGVHD in the U.S., the registration study (KD025-213) met clinical endpoints and supported the conclusion that benefits outweighed risks. A rolling submission NDA for the cGVHD indication based on this study was also completed at the end of November 2020 and was fully approved by the FDA on July 16, 2021 in the United States. Given the global development status of BN101/belumosudil in the cGVHD indication, and based on the recommendation of the NMPA, we first conducted a PK bridging clinical trial in healthy volunteers to initially assess the safety, drug exposure and metabolites of BN101/belumosudil in healthy individuals to determine the BN101/ belumosudil starting dose and PK profile. Given that the PK bridging clinical trial in healthy volunteers has been substantially completed and met the bridging objective, the Sponsor currently plans to conduct a bridging study to evaluate the efficacy, safety and PK characteristics of BN101/belumosudil for the treatment of Chinese patients with cGVHD. This bridging study is an open, single-arm trial in Chinese patients with cGVHD, and because it is designed for bridging purposes, the sample size is not determined by statistical assumptions.

This study is planned to enroll 30 patients with cGVHD who have undergone at least 1 but not more than 5 lines of systemic therapy. Considering that the recommended dose of both cGVHD clinical trials in Western populations was 200 mg QD and the highest administered dose of BN101/belumosudil in the phase I dose-escalation study reached 1000 mg QD/500 mg BID and

was well tolerated, combined with the pharmacokinetic profile of 200 mg orally in the phase I study in Chinese healthy volunteers was consistent with the results in the overseas study, without any TEAE associated with the investigational drug, the starting dose of this cGVHD bridging clinical trial was also set at 200 mg QD.

2. STUDY OBJECTIVES/PRUPOSE

Primary Objective:

• To evaluate the efficacy and safety of BN101/belumosudil in subjects with cGVHD who had previously been treated with at least 1 prior line of systemic therapy.

Secondary Objectives

- To evaluate the PK profile of BN101/belumosudil in subjects with cGVHD who had previously been treated with at least 1 prior line of systemic therapy;
- To evaluate other efficacy endpoints of BN101/belumosudil in subjects with cGVHD who had previously been treated with at least 1 prior line of systemic therapy.

Exploratory Objective

 To evaluate changes in the Patient-Reported Outcomes (PRO) Measurement Information System (PROMIS) Global Health sub-scores of physical and mental functioning.

3. STUDY POPULATION

3.1 Inclusion Criteria

Subjects who met all of the following conditions could be enrolled in the study:

- (1) Male or female subjects aged \geq 18 years who have had allogeneic hematopoietic stem cell transplant (allo-HSCT).
- (2) Have persistent cGVHD manifestations and systemic therapy is indicated.
- (3) Previously received at least 1 and not more than 5 lines of systemic therapy for cGVHD².
- (4) Receiving glucocorticoid therapy with a stable dose over the 2 weeks prior to screening; or 4 weeks of prednisone or equivalent doses of other corticosteroids at doses > 0.5 mg/kg/day with persistent manifestations of cGVHD and no improvement; or 2 attempts to reduce the hormone to a lower

Protocol Version 3.0 Version Date: 25 Feb 2022

² The following approach should be used when documenting prior cGVHD treatment:

[•] The initiation of one or more new systemic therapies for cGVHD will be considered the initiation of a new first-line treatment

If multiple medications are intended to be initiated at the same time, the dates of initiation of treatment
with different medications may be spaced up to 4 weeks apart due to schedule delays or medication
availability

Topical medications are not considered a line of therapy

dose level fail and the prednisone dose still needs to be increased to > 0.25 mg/kg/day or an equivalent dose.

- (5) Eastern Cooperative Oncology Group (ECOG) performance status (PS) score: 0 to 1.
- (6) Life expectancy of more than 12 months.

General Criteria

- (7) Female subjects of childbearing potential have a negative serum pregnancy test at screening. Females of childbearing potential are defined as sexually mature females without prior hysterectomy or who have had any evidence of menses in the past 12 months. However, females who have been amenorrheic for 12 or more months are still considered to be of childbearing potential if the amenorrhea is possibly due to prior chemotherapy, anti-estrogens, or ovarian suppression.
- (8) Sexually active females of childbearing potential enrolled in the study must agree to use two forms of accepted methods of contraception during the course of the study and for 3 months after their last dose of study drug. Effective birth control includes:
 - Intra-uterine contraceptive device plus 1 barrier method;
 - Stable doses of hormonal contraception (e.g., oral, injectable, subcutaneously implanted, transdermal) for at least 3 months plus 1 barrier method;
 - Two barrier methods. Effective barrier methods are male or female condoms, diaphragms, and spermicides (creams or gels that contain a chemical to kill sperm); or
 - A vasectomized partner.
- (9) For male subjects who are sexually active and who are partners of females of childbearing potential: must agree to use 2 recognized methods of contraception during the treatment period and for 3 months after the last dose of study drug (see criterion 8 above).
- (10) Subject (or the subject's legally authorized representative) must be fully informed of the study contents and is able to provide written ICF prior to any study-specific procedures, and is willing to follow the treatment regimen and visit schedule.

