4.3.1 Screening/baseline period (-14 days \sim -1 day)

The screening period begins with the signing of the ICF. The ICF must be signed before any study-required or study-related operation, procedure, or assessment is performed. Patients must be given sufficient time to ask questions and make voluntary decisions before signing the ICF.

Data on screening failures also need to be recorded in the electronic data capture (EDC) system.

Unless otherwise specified, the Screening Period Assessment Program was to be completed within 14 days prior to the first administration of study drug. Subjects who meet all inclusion criteria while not meeting any of the exclusion criteria may be enrolled in the study. Subjects' eligibility for enrollment must be confirmed by the sponsor's Medical Director or Contract Research Organization (CRO) medical monitor prior to administration of study drug. Subjects who fail screening are permitted to be rescreened 1 time with the approval of the Medical Monitor; however, candidate subjects who fail screening because of abnormal laboratory indicators may not be rescreened after medical intervention. Subjects undergoing rescreening must sign a new ICF and be given a new screening number, and are permitted to receive the test(s) for which they passed the previous screening if they passed the previous screening test and are within the time window for this screening.

The procedures and assessments for the specific screening period are as follows:

- 1) Obtain written informed consent;
- 2) Demographic information (including gender, age/date of birth, ethnicity);
- 3) Past medical history;
- 4) History of transplantation (including indications for transplantation and type of transplantation);
- 5) History of GVHD (acute and chronic);
- 6) History of cGVHD treatment (including previous lines of therapy for cGVHD);
- 7) cGVHD severity assessment (-7 days to -1 day);
- 8) Full physical examination (including height);
- 9) Vital signs (including temperature, respiratory rate, sitting blood pressure and pulse);
- 10) weight and body mass index (calculated from height and weight: BMI = weight (kg)/height² (m²));
- 11) ECOG PS score;
- 12) blood routine, urinalysis, blood biochemistry (-7 days to -1 day);
- 13) Virology;
- 14) 12-lead ECG (supine position);
- 15) Echocardiogram [left ventricular ejection fraction (LVEF)];
- 16) Serum pregnancy test (-7 days to -1 day, for women of childbearing age only);

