- 9. Virology includes Hepatitis B Surface antigen (HBsAg), Hepatitis B Surface Antibody (HBsAb), Hepatitis B core antibody (HBcAb), Hepatitis Be antigen (HBeAg), Hepatitis Be antibody (HBeAb), Hepatitis C antibody (HCV-Ab), human immunodeficiency virus (HIV) antibody, Hepatitis B virus DNA (HBV-DNA) (if applicable), Hepatitis C virus RNA (HCV-RNA) (if applicable). If they are done at the site within 28 days prior to screening and reports can be provided, the investigator determines that the test can be used as a result of the screening period. When HBcAb or HCV-Ab is positive, HBV-DNA or HCV-RNA should be tested to rule out active infection.
- 10. 12-Lead ECG see ECG Assessment table.
- 11. Female of childbearing age are tested for pregnancy. For this study, the reproductive age was defined as non-menopausal, and menopause included natural amenorrhea ≥12 months; Or natural amenorrhea ≥24 months after chemotherapy; Or natural amenorrhea ≥6 months and serum follicle-stimulating hormone (FSH) level > 40 IU/L; Or confirmed surgical records and/or pathology reports confirmed after bilateral oophorectomy. Serum pregnancy tests for women of childbearing age during the screening period must be negative. Urine pregnancy test can be performed as needed during the study treatment. Positive results are to be confirmed with serum testing. If the urine pregnancy result is positive, subjects should stop the study drug treatment and withdraw from the study, and the investigators will continue to follow up subjects until delivery and 30 days after delivery. Subjects who did not deliver were followed up until the end of the pregnancy.
- 12. On Day 1 of Cycles 1 to 7, subjects will take their dose at the clinic and then will be dispensed study drug for home administration. Instruct subjects to fill in the study drug dairy. From Cycle 8 onwards, the Day 1 dose may be taken at home or in the clinic.

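### Inclusion criterion 7 and Appendix 1 note 11 define women able to conceive differently, so a woman 24 months amenorrhoeic, possibly from chemotherapy, must use contraception but is not listed for pregnancy tests (minor)

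*Protocol*

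**What the plan says.** **Criterion 7** (Protocol 3.1, repeated in the synopsis) requires a negative serum test at screening in women of childbearing potential. It describes them as "sexually mature females without prior hysterectomy or who have had any evidence of menses in the past 12 months". It adds that a woman without periods for 12 months or more is "still considered to be of childbearing potential if the amenorrhea is possibly due to prior chemotherapy, anti-estrogens, or ovarian suppression". No upper limit on time is given.

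**Criterion 8** ties contraception to the same term: "Sexually active females of childbearing potential enrolled in the study must agree to use two forms of accepted methods of contraception".

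**Appendix 1 note 11**, attached to the pregnancy-test row of the schedule, gives a second definition: "For this study, the reproductive age was defined as non-menopausal". Its menopause list starts with natural amenorrhoea of at least 12 months and continues "Or natural amenorrhea ≥24 months after chemotherapy; Or natural amenorrhea ≥6 months and serum follicle-stimulating hormone (FSH) level > 40 IU/L". It ends with a surgical limb: "Or confirmed surgical records and/or pathology reports confirmed after bilateral oophorectomy".

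**Who is tested.** Section 8.5 limits pregnancy testing to women of *childbearing age*. The visit lists use the same term, for example 4.3.1 item 16: "Serum pregnancy test (-7 days to -1 day, for women of childbearing age only". The urine tests in 4.3.2.1, 4.3.3, 4.3.4 and 4.3.5 carry the same restriction. Only note 11 explains the term.

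**How firm the urine tests are.** Section 8.5 makes them optional after screening, and note 11 says "Urine pregnancy test can be performed as needed during the study treatment".

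**The concern.** One woman can fall on both sides of the line. If her periods stopped 24 months or more ago and chemotherapy may be the reason, the eligibility criteria treat her as able to conceive, while the testing schedule treats her as menopausal.

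This matters because Protocol 1.3 reports embryo-fetal toxicity in rats and rabbits, and section 8.9 requires the drug to be stopped as soon as a subject becomes pregnant. Stopping depends on detection. By inference, not stated in the protocol, a woman who already has no periods cannot notice a missed one.

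Such women are plausible here. Every subject has had an allogeneic transplant (criterion 1), and SAP 8.3.5 records myeloablative or nonmyeloablative conditioning. Sections 3.1 and 3.2 set no limit on time since transplant or chemotherapy.

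**Working it through.** The plan gives no figure to reproduce. The check is to apply both definitions to the same women, then count the listed tests.

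**Step 1. The definitions side by side**

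| Woman | Criterion 7 | Note 11 |
|---|---|---|
| Uterus and ovaries, 30 months of amenorrhoea, chemotherapy a possible cause | Childbearing potential (no time limit) | Menopausal (24-month limb) |
| Uterus and ovaries, 8 months of amenorrhoea, FSH above 40 IU/L | Childbearing potential (menses within 12 months) | Menopausal (FSH limb) |
| Hysterectomy more than 12 months ago, ovaries kept, no other cause of amenorrhoea | Not of childbearing potential | Not menopausal, so counted, if the list is complete |

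The first row is the point made here. It holds whether the *or* in criterion 7 is read literally or as *and*, because the chemotherapy sentence brings her in either way.

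**Step 2. Does note 11's word *natural* take her out of the 24-month limb?** If it excluded amenorrhoea that chemotherapy may have caused, the limb would add nothing, since natural amenorrhoea of 12 months already counts as menopause. The limb does some work only if women after chemotherapy are a separate case with a longer wait. The evident reason for a longer wait is that chemotherapy may have stopped the periods.

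**Step 3. Tests for which she is not listed.** These are the screening serum test in 4.3.1 item 16 and the urine tests from C2D1 to the 28-day follow-up. The C1D1 urine test is not counted: 4.3.2.1 waives it after a serum test in the previous 7 days, and the screening window is days -7 to -1.

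Inputs: 28-day cycles; odd cycles only after C7 (note 14); main study ends 12 months after the last enrolment (note 13); enrolment estimated at 6 months (SAP 4). Day 1 of cycle n = 1 + (n − 1) × 28.

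- Over 12 months (day 365): C2 to C7 = 6 visits. C13D1 = 1 + 12 × 28 = 337 falls inside and C15D1 = 1 + 14 × 28 = 393 outside, so C9, C11 and C13 = 3. With EOT and the 28-day visit: 6 + 3 + 2 = 11.
- Over 6 + 12 = 18 months (about day 548, earliest enrolees): C19D1 = 1 + 18 × 28 = 505 falls inside and C21D1 = 1 + 20 × 28 = 561 outside, so C9 to C19 odd = 6. Total: 6 + 6 + 2 = 14.

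These are the largest possible numbers of listed urine tests. They need treatment to run almost to the end of the period, with the last dose early enough for the 28-day visit to fall inside it.

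**The case against.** The strongest reply is that almost nothing is lost. No woman is assured a urine test after screening, so being off the list costs at most a prompt. The main protections cover this woman: criterion 7 requires her serum test, criterion 8 requires two contraceptive methods until 3 months after the last dose if she is sexually active, and 4.3.1 requires eligibility to be reviewed and confirmed by the sponsor's or CRO's medical staff before dosing. Section 4.3.7 allows unscheduled visits on clinical need. All of this stands, and it sets the grade.

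A second reply concerns *natural*. The 24-month limb could be read as a longer wait for a natural menopause that follows chemotherapy but is not caused by it. She would then stay in both groups. That reading is possible but strained, since a site could rarely tell the two apart, and the text does not say it. The FSH row of the table would still conflict.

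Some stronger readings are tempting but not supported:

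- **That she could enter untested.** Criterion 7 governs entry, and without the serum result she does not meet it. What is left is two contradictory site instructions.
- **That she is deprived of 11 to 14 tests.** Those are listed maxima of discretionary tests.
- **That criterion 7 sweeps in every postmenopausal woman with a uterus.** Its *or* can be read that way, but the sentence on amenorrhoea makes sense only if other women with 12 months of amenorrhoea are excluded. This is loose drafting.
- **That counting hysterectomised women is a fault of consequence.** At worst one is listed for a test she does not need.
- **That the urine tests must become mandatory.** Section 8.5 and note 11 agree that they are discretionary. Changing that is a separate option and does not follow from the mismatch.

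**Conclusion.** The inconsistency is real and nothing in either document reconciles it. A woman with uterus and ovaries, amenorrhoeic for 24 months or more and possibly because of chemotherapy, is of childbearing potential for eligibility and contraception but menopausal for testing.

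Severity is minor. The practical effect is a contradictory instruction about the screening serum test, and no listed test for her at visits where other women have one. The number of such women cannot be worked out from the documents and may be zero. Efficacy results and analysis sets are not affected.

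The conclusion rests on two readings: that note 11's 24-month limb includes amenorrhoea that chemotherapy may have caused, and that *childbearing age* in 8.5 and the visit lists means what note 11 says.

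**What to change.** Use one term, *childbearing potential*, and one definition in criterion 7 (synopsis and 3.1), note 11, section 8.5 and sections 4.3.1 to 4.3.5. Suggested wording: a woman is of childbearing potential unless she has had a hysterectomy or bilateral oophorectomy, or has had 12 months or more of amenorrhoea for which chemotherapy, anti-estrogens and ovarian suppression are not possible causes.

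Delete note 11's 24-month limb and its FSH limb. FSH is in neither Table 5 nor the schedule, so the trial does not collect it. Copying criterion 7 unchanged would carry over its loose *or*, so the new wording should replace both texts.

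The cost is a wording amendment and a few extra inexpensive urine tests at existing visits, some in women who cannot conceive. The ceiling per added woman is the 11 or 14 listed tests counted above, and fewer if the tests stay discretionary.

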3.2 Exclusion Criteria

Subjects who met any of the following conditions would be excluded from the study:

(1) Received a systemic investigational cGVHD treatment within 28 days of study entry, but prior treatment is allowed with a washout of at least 28 days or 5 half-lives.[Note: Corticosteroids, CNIs, sirolimus, mycophenolate mofetil (MMF), methotrexate, azathioprine, and *in vitro* photochemotherapy (ECP) are acceptable and subjects must have been on a stable dose/regimen of these for at least 2 weeks prior to screening].

- (2) Recurrence of hematologic tumor (according to criteria for recurrence of the corresponding primary hematologic tumor) or post-transplant lymphoproliferative disease at screening.
- (3) Current treatment with ibrutinib (except for ibrutinib with a washout of at least 28 days prior to the first dose of the investigational product).

Laboratory Tests

- (4) Absolute neutrophil count (ANC) $< 1.5 \times 10^9$ /L.
- (5) Platelet count $< 50 \times 10^9/L$.
- (6) Alanine aminotransferase (ALT) $> 3 \times \text{upper limit of normal (ULN)}$, aspartate aminotransferase (AST) $> 3 \times \text{ULN}$
- (7) Total bilirubin (TBIL) $> 1.5 \times ULN$.
- (8) Creatinine clearance (CrCl) < 60 mL/min (Cockcroft-Gault formula).

General Criteria

- (9) Pregnant or lactating women.
- (10) History of severe illness, or other evidence of severe illness, or any other conditions that would make the subject, in the opinion of the investigator, unsuitable for the study
- History of severe [New York Heart Association (NYHA) functional class III or IV] cardiovascular disorder, including but not limited to ventricular arrhythmias requiring clinical intervention, uncontrolled hypertension (systolic blood pressure ≥ 160 mmHg and/or diastolic blood pressure ≥ 100 mmHg); unstable angina pectoris, acute coronary syndrome, congestive cardiac failure, stroke, or other ≥ Grade 3 cardiac events within 6 months prior to enrollment; and NYHA functional class ≥ II or left ventricular ejection fraction (LVEF) < 50% by cardiac ultrasound at screening.

- Inability to take oral medications, severe (NCI CTCAE v5.0≥ Grade 3) chronic gastrointestinal dysfunction, malabsorption syndrome, or any other condition that affects gastrointestinal absorption.
- History of clear neurological or mental disorders (including epilepsy or dementia), current mental disorders, or poor compliance that rendered the subject ineligible for participation in the study as judged by the investigator.
- History of other serious (NCI CTCAE v5.0≥ Grade 3) systemic disease that rendered the subject ineligible for participation in the clinical trial as judged by the investigator.
- (11) Known active hepatitis B virus (HBV) or hepatitis C virus (HCV) infection, or human immunodeficiency virus (HIV) infection. [Note: Active HBV infection is defined as positive for serum hepatitis B virus surface antigen (HBsAg) and/or hepatitis B virus e antigen (HBeAg), or HBV-DNA; subjects with positive hepatitis B virus core antibody (anti-HBc)

should be confirmed for HBV-DNA, and subjects who are confirmed to be negative for HBV-DNA could be enrolled; active HCV infection is defined as positive for HCV-RNA, and subjects who are positive for hepatitis C virus antibody (HCV-Ab) could only be enrolled after confirmed to be negative for HCV-RNA. Positive is defined as \geq the ULN].

- (12) Diagnosed with another primary malignancy (other than malignancy for which allo-HSCT was performed) within 3 years of enrollment, with the exception of:
- Completely resected basal cell or squamous cell carcinoma of the skin;
- Surgically cured carcinoma in situ of the cervix;
- Resected breast ductal carcinoma in situ;
- Prostate cancer with Gleason score < 6 and stable prostate-specific antigen (PSA) over 12 months.
- (13) Known allergy to the active ingredient or excipients of the investigational product, or any other selective ROCK2 inhibitors.
- (14) Subjects requiring long-term proton pump inhibitors (e.g., rabeprazole, omeprazole) or CYP3A4 inducers (e.g., rifampin, phenobarbital).
- (15) Prolongation of QT interval corrected by the Fridericia's formula (QTcF) of > 450 ms for males and > 470 ms for females at screening.
- (16) Known alcohol or drug dependence.
- (17) Forced expiratory volume in 1 second (FEV₁) \leq 39% or pulmonary function score of 3 at screening.
- (18) Treatment with any investigational agent, device, or procedure, within 28 days (or 5 half-lives, whichever is longer) prior to enrollment.
- (19) Subjects considered unlikely to adhere to treatment and follow protocol in the opinion of the investigator.

3.3 Criteria for completion of study drug therapy and early termination of study drug therapy

Eligible subjects will be enrolled to receive BN101/belumosudil (every 28-day cycle) until cGVHD progression [Evaluated by the investigator based on the National Institutes of Health (NIH) Consensus Development Project on Criteria for Clinical Trials in cGVHD(2014) diagnosis and staging, and response criteria, hereinafter referred to as the NIH Consensus Criteria (2014)], intolerable toxicity, initiation of a new cGVHD therapy, recurrence of hematological neoplasm (according to the recurrence criteria of the corresponding primary hematologic tumor), loss to follow-up, withdrawal of consent, or death, etc., whichever occurred first.

For subjects assessed as "Lack of Response - Mixed" and "Lack of Response - Progression" (See

section 7.1.1, table 4), if the investigator believed that these subjects could continue to benefit from treatment with BN101/belumosudil, the treatment may be continued after a written application was submitted, and approval from the Sponsor's Medical Director as well as documentation of the subject's willingness to continue treatment was obtained. In such cases, the rationale for continuing treatment must be clearly documented. In addition, "Lack of Response - Mixed" will be considered a progression event in the analysis of outcomes.

For subjects who did not achieve any response after 12 cycles of BN101/belumosudil treatment during the main study (the end of the main study is defined in section 3.5 of the main body), they should discontinue the investigational product treatment and withdraw from the study if they were judged by the investigator to have no clinical benefit (e.g., improvements in organ score, improvements in Lee symptom scores, reductions of corticosteroid/tacrolimus doses).

(1) Completion of study drug therapy

- Completion of study drug therapy as defined by the protocol;
- cGVHD disease progression during treatment;
- Death of the subject.

(2) Early termination of study drug therapy

Refers to the situation in which an enrolled subject becomes unfit to continue treatment with the study drug during the course of the study. Early termination of study drug treatment is defined as follows:

- Recurrence of the subject's hematologic tumor during the course of the trial (according to the criteria for recurrence of the corresponding primary hematologic tumor).
- The subject is discontinued due to an adverse event or serious adverse event that makes continuation of study drug treatment inappropriate; or the subject is discontinued due to an adverse event or serious adverse event for more than 14 days.
- The investigator determines that the subject's continued treatment with the study drug may pose a potential risk greater than benefit to the subject, including: pregnancy; enrollment in the study and discovery that the subject does not meet the study protocol inclusion criteria and that continued treatment with the study drug poses a risk greater than benefit to the subject; failure to follow the protocol or doctor's orders, unauthorized use of other treatments, or failure to take the medication in a timely manner and at a dosage that would interfere with the assessment of efficacy and increase potential safety risks.
- Subject withdraws informed consent/withdraws from the study.
- Subject lost to follow-up.

After discontinuation of study medication, subjects will undergo end-of-treatment visits and enter

a safety follow-up period (including a 28-day follow-up after the last dose and a long-term safety follow-up).

Subjects have the right to withdraw from the study at any stage of the study under the terms of informed consent, or to be "withdrawn" (or "dropped") from the study even if they do not explicitly withdraw from the study but no longer accept the study medication or the study evaluations. The reasons for withdrawal should be understood and documented to the extent possible, e.g., perceived intolerance of certain AEs associated with the study drug, other reasons for not being able to continue in the clinical study, or unexplained loss of visits.

(3) Treatment of withdrawn subjects

The investigator must complete the reason for the subject's withdrawal from the study on the electronic case report form (eCRF) and contact the subject to complete the evaluation program for the end-of-treatment visit (EOT) and safety follow-up (28 ± 7 days after the last dose of study drug or prior to initiation of a new treatment for systemic cGVHD) whenever possible, and keep records, documenting, whenever possible, the time of the subject's last dose of study drug. The eCRF should be retained for subjects who withdraw from the trial for whatever reason.

During the main study, after a subject terminates study treatment, the investigator must follow up on all pre-existing AEs and SAEs that occurred during the Safety Follow-Up Period [28 ± 7 days after the last dose of study drug or prior to initiation of new treatment for systemic cGVHD, whichever occurs first], report on new AEs and SAEs (whether or not related to the study drug) occurring during this period, with SAEs and AEs related to the study drug to be followed up until resolution of the AE and SAE, and until, in the investigator's opinion, the event is stabilized or irreversible. Any SAE is required to follow the SAE Reporting Procedures (see Section 8.6.2.2) and contact the sponsor in a timely manner.

